11.3 Secondary Objective

Daily “pain score right now” and “pain score average last 24 hours” will be compared between the gabapentin and place groups using longitudinal models, with pain treatment group and if necessary, other clinical factors as explanatory variables. For “pain score right now”, time since last morphine use will be used as an explanatory variable as well. The pain scores are discrete, thus a proper link function (such as Poisson) will be applied.

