Randomization: Patients with ALL on Total XVI or “as per TOTXVI” who experience NP/PN after certain doses of vincristine are eligible to enroll in the study as soon as the diagnosis of NP/PN related to VCR is established. Participants will be randomized to receive gabapentin or placebo and continue taking the study drug until 2 doses of vincristine have been completed, and for 7 days after the second dose of vincristine. Morphine will be available to both groups as needed for pain at any time on the study.

Data Analyses: Two efficacy measurements will be analyzed: the average daily morphine dosage and the average daily pain score during the maximum 21-day treatment period. We will test the null hypothesis that the expected average daily morphine dosage and pain score are the same in the gabapentin and the placebo group vs. a one-sided hypothesis that the expected average daily morphine dosages and pain scores are lower in the gabapentin group.

Anticipated Primary Completion Date: December 2016

Anticipated Study Completion Date: December 2018

Timeframe for Primary Outcome Measure:

Data Management: Data management and statistical analysis will be provided locally by the Department of Anesthesiology and Biostatistics Department at St. Jude Children’s Research Hospital, respectively.

Human Subjects: The risk to subjects is related to the side effects of gabapentin. The most common side effect is somnolence. Patients will be informed of this and other minor side effects during informed consent. Adverse events will be monitored and reported and treated appropriately.

Table of Contents

List of Collaborating Investigators/Institutions Protocol Summary

1.0	OBJECTIVES	1
1.1	Primary Objective.....	1
2.0	BACKGROUND AND RATIONALE	1
2.1	Background	1
2.2	Rationale.....	2
3.0	RESEARCH PARTICIPANT ELIGIBILITY CRITERIA AND STUDY ENROLLMENT	3
3.1	Inclusion Criteria.....	3
3.2	Exclusion Criteria.....	4
3.3	Research Participant Recruitment and Screening	4
3.4	Enrollment on Study.....	4
3.5	Procedures for Identifying and Randomizing Research Participant.....	5
4.0	TREATMENT PLAN	6
4.1	Study Treatment	7
4.2	Breakthrough Pain Control.....	7
4.3	Dose Modifications	8
4.4	Definitions of Dose-Limiting Toxicity.....	8
4.5	Concomitant Therapy	8
4.6	Supportive Care	8
5.0	DRUG INFORMATION	8
5.1	Gabapentin (Neurontin).....	8
5.2	Placebo.....	9
6.0	REQUIRED EVALUATIONS, TESTS, AND OBSERVATIONS	10
6.1	Pre-Study Evaluations	10
6.2	Evaluations during Therapy	10

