Appendix I: Example of a schedule of evaluations

Appendix II: Research Activities

Appendix III: Pain Scales

1.0 **OBJECTIVES**

The investigators propose to study the analgesic efficacy of gabapentin for the treatment of neuropathic pain/peripheral neuropathy (NP/PN) associated with vincristine therapy in the context of treatment of childhood ALL on Total XVI protocol.

1.1 **Primary Objective**

To assess the analgesic efficacy of gabapentin in controlling VCR-related NP/PN in participants with ALL, by comparing the morphine daily dose (mg/kg/day) used to control NP/PN as a primary or a rescue regimen in the gabapentin vs. placebo groups.

1.2 **Secondary Objective**

To compare the pain scores in the gabapentin and placebo groups as recorded by pain score right now and pain score average for previous 24 hours.

2.0 **BACKGROUND AND RATIONALE**

2.1 **Background**

Children with cancer experience a significant symptom burden during the course of treatment^{1,2}, and pain is the most frequent, most severe and most distressful of symptoms. The impact of pain experienced during treatment for cancer has long term implications after completion of therapy^{3,4}.

Neuropathic pain and related neuropathy symptoms have been directly correlated with chemotherapeutic agents⁵, vincristine in particular⁶ and have been reported during therapy for childhood cancers^{7,8}.

Neurotoxicity, the dose-limiting side effect of vincristine, most often causes mixed sensorimotor neuropathy (loss of deep tendon reflexes, paresthesias, neuritic pain, and wrist or foot drop) or autonomic neuropathy (constipation, abdominal pain, paralytic ileus, bladder atony with retention of urine, and orthostatic hypotension). On the rare occasions in which vincristine-associated neurotoxicity involves the cranial nerves, it produces transient cortical blindness, oculomotor nerve dysfunction with ptosis and diplopia, jaw pain, facial palsy, hearing loss, and vocal cord paresis or paralysis⁵.

The incidence of peripheral neuropathy related to vincristine during treatment of childhood ALL per protocol Total XIIIB in our institutional experience has been 17.5% (42 of 240)⁹ and peripheral neuropathy/neuropathic pain were identified as adverse events in 34.9% of

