4.2 Breakthrough pain control

All participants, regardless of treatment assignment, will receive open-label oral morphine (0.15 mg/kg/dose every 2 hours, **rounded to the nearest tablet size or measurable liquid quantity**), as needed for pain. Morphine orders and dosages will be managed by the pain team according to clinical indication and following institutional and pharmacy policy for prescription and administration of controlled substances.

Substitution of other opioids for morphine should be avoided and performed only upon consultation with the PI.

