11.0 STATISTICAL CONSIDERATIONS

11.1 Primary Objective

This study has the following single primary objective:

To assess the analgesic efficacy of gabapentin in controlling VCR-related NP/PN in participants with ALL, as reflected by the morphine daily dose (mg/kg/day) used to control NP/PN as a primary or a rescue regimen, and by daily pain scores in the gabapentin vs. placebo groups.

Accrual: The eligibility criteria requires that a patient can be enrolled in this study only if a VCR-induced NP not previously treated by gabapentin occurred after vincristine doses administered at the following time points: Induction Week 1 ± 3 days, Induction week 2 ± 3 days, Continuation Week 7 (Re-induction I) ± 3 days or Week 17 (Re-induction II) ± 3 days of Continuation. A review of Total XVI or “as per TOTXVI” patients up to the date of this protocol development showed that respectively 33, 29, 5, and 1 patient satisfied the condition at the time points. A review of Total XV showed a similar pattern. Thus we expect to enroll for this study at least 60 patients in the remainder of Total XVI or “as per TOTXVI. We will enroll and randomize all eligible and consented patients in the remainder of Total XVI or “as per TOTXVI”. To achieve a total of 60 evaluable patients, up to 80 participants may be enrolled.

Study Design: Placebo-controlled, randomized Phase-II trial. Sixty (60) participants will be randomized into the treatment (gabapentin) and the placebo group, with 30 patients per group.

Analysis: For each subject a pre-treatment (baseline) pain score will be obtained from the leukemia clinic. This score serves as the baseline level of pain and is used in stratified randomization (see below); and if necessary, as a covariate in modeling the daily morphine dosage used for pain control. The daily morphine dosage will be modeled as longitudinal observations with treatment (gabapentin vs. placebo) group, and if necessary, other clinical factors such as age category for pain assessment (0-3yr, 4-7yr, >7yr), baseline pain score, and ALL risk classification, as explanatory factors, using repeated measure linear models.

Multiple test adjustment will not be made. Participants **whose doses of vincristine are delayed or those who are taken off study drug** will be included in the analysis according to “intent to treat”.

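### Section 11.3 forces time since last morphine, a post-randomisation variable, into the model for current pain, so its treatment coefficient is not the randomised comparison that the objective states

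*Combined protocol and SAP*

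**What the plan says.** Section 1.2 gives the secondary objective: "To compare the pain scores in the gabapentin and placebo groups as recorded by pain score right now", and also by the 24-hour average. Section 11.1 puts pain into the primary objective too, by adding "by daily pain scores in the gabapentin vs. placebo groups".

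The protocol summary (Data Analyses) names two efficacy measures: "the average daily morphine dosage and the average daily pain score during the maximum 21-day treatment period". Its null hypothesis is that "the expected average daily morphine dosage and pain score are the same in the gabapentin and the placebo group", and the alternative is "a one-sided hypothesis that the expected average daily morphine dosages and pain scores are lower in the gabapentin group".

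Section 11.3 compares both pain scores by longitudinal models, with a Poisson link given as an example. Treatment group is in the model, and other clinical factors are added only where needed. For the current score alone there is a further, unconditional instruction: "time since last morphine use will be used as an explanatory variable as well".

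On morphine, the summary (Randomization) says "Morphine will be available to both groups as needed for pain at any time on the study", and section 4.2 says "All participants, regardless of treatment assignment, will receive open-label oral morphine", to be taken as needed. Section 1.1 makes the daily morphine dose the primary outcome.

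**The concern.** Time since last morphine is measured after randomisation. Morphine is taken in response to pain, and the trial's own hypothesis is that gabapentin reduces both. The covariate can therefore be changed by treatment, and it also depends on the outcome being modelled. Holding it fixed removes part of what treatment does and mixes children whose underlying pain differs.

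The objective and the hypotheses are stated as plain group comparisons, and nowhere do the documents say that the effect of interest is conditional on morphine timing. Because 11.3 makes the covariate mandatory, following the plan as written yields only the conditional estimate for this score. A reader would take it as the randomised effect on current pain, and could be wrong about its size or even its direction.

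**Working it through.** **No stated figure to reproduce.** The documents give no pain SD, morphine rate, effect size or significance level. The 60 patients (30 per group) come from expected accrual. The check is therefore algebra, followed by simulation on assumed inputs.

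**Algebra.** Let Z be treatment (1 = gabapentin), Y the current score and T the time since last morphine. The objective is Δ = E[Y|Z=1] − E[Y|Z=0]. Section 11.3 fits, apart from the link, E[Y|Z,T] = β0 + β1·Z + β2·T. For a linear model with these terms,

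Δ = β1 + β2·(E[T|Z=1] − E[T|Z=0]).

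So β1 equals Δ only if T has no slope or its mean is the same in both groups. If gabapentin reduces morphine use, T would be expected to be longer on gabapentin. The sign of β2 then sets the direction:

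- If children in more pain have dosed more recently, β2 is negative and β1 lies closer to zero than a beneficial Δ.
- If the main feature is relief wearing off, β2 is positive and β1 lies further from zero.

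The documents do not settle which dominates.

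**First simulation (all inputs assumed).** There were 2,500 patients per group with 13 daily readings, analysed by Poisson GEE with independence correlation and treatment only, then with T added. Mean latent pain was 4, between-patient SD 1 or 2, effect 1.5 points, peak relief 1, 2 or 4 points, relief half-life 3 or 8 h, and T capped at 48 h, giving 12 scenarios.

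- Mean T was about 8 to 15 h on placebo and 18 to 23 h on gabapentin.
- The ratio of mean scores was 0.63 to 0.70 without T and 0.60 to 0.80 with it.
- The slope of T was negative in 10 scenarios, where the ratio moved towards 1 (for example 0.627 to 0.786). It was positive in 2, where the ratio moved away (for example 0.670 to 0.596). This matches the algebra.
- With no treatment effect, the two ratios differed by at most about 0.012 and stayed near 1.

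**Second simulation (all inputs assumed).** There were 8 batches of 2,000 patients over 16 days in hourly steps, with one score a day at a random hour from 8 to 17. Latent pain had mean 4.5, between-patient SD 2.2 (0.5 in setting 4), within-patient SD 1.3 per day and a latent effect of −1.0. The score was latent pain minus relief, clipped to 0–10 and rounded. Doses were at least 2 h apart, and relief added up and decayed exponentially. The fit was a linear GEE, exchangeable, with baseline pain and T linear in hours. The simulated dosing behaviour was:

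1. Rate 0.06·exp(0.55·pain) per day; relief 3; time constant 3 h.
2. Dose probability 0.5 per hour at pain ≥3.5; same relief.
3. Probability 0.95 per hour at pain ≥3.5; relief 5; time constant 6 h.
4. As setting 3, with threshold 3 and between-patient SD 0.5.

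T is undefined before a child's first dose and 11.3 gives no rule, so three codings were used. Entries are treatment differences in points.

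| Setting | Without T | T, such scores dropped | T capped at 24 h | T with no-dose indicator |
|---|---|---|---|---|
| 1 | −0.823 | −0.790 | −0.807 | −0.798 |
| 2 | −0.580 | −0.450 | −0.468 | −0.472 |
| 3 | −0.168 | −0.054 | −0.332 | −0.124 |
| 4 | +0.065 | −0.075 | −0.233 | −0.081 |

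Relative change:

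- Setting 1: 2–4% smaller (for example 0.790/0.823 = 0.96).
- Setting 2: 19–22% smaller (0.450/0.580 = 0.78).
- Setting 3: from 68% smaller (0.054/0.168 = 0.32) to 98% larger (0.332/0.168 = 1.98).
- Setting 4: the sign changes.

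The model matters as well. Setting 1 with treatment only and independence correlation gave −0.764, then −0.498 / −0.542 / −0.496, which is 29–35% smaller. With no effect of gabapentin, adding T moved the estimate by at most 0.005 points in settings 1 and 4.

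**Rejection rates.** For 60-patient trials with the Poisson model and an assumed one-sided 0.05 level, the rates without T, then with the three codings, were:

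- Setting 1: 0.906; 0.888 / 0.904 / 0.905.
- Setting 2: 0.909; 0.797 / 0.860 / 0.874.
- Setting 3: 0.361; 0.141 / 0.740 / 0.333.

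**The case against.** The strongest reply has four parts.

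**Limited reach.** Only one of two scores under a secondary objective is affected. The 24-hour average is modelled in the same section without the covariate, so a randomised pain comparison is already planned, and the morphine model is untouched. With no effect on pain or morphine, the simulations show no distortion. All of this stands, and it bounds the importance of the point.

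**Soft magnitudes.** Every input is assumed. The 98% figure arises only from the 24 h cap. With the no-dose indicator the shifts in settings 1 to 4 are 0.025, 0.108, 0.044 and 0.146 points. The sign change needs a narrow patient spread and near-certain dosing. Repeat runs of setting 2 gave −0.60 and −0.66 without T, against −0.580, with similar proportional shifts. This also stands: no single size should be relied on. But the coding problem belongs to the plan, which requires a covariate that is undefined for some scores and gives no rule for them.

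**Recent analgesia matters for an instantaneous score.** In setting 4 the comparison without T is +0.065 although latent pain falls by 1.0, because rescue morphine masks the benefit. The motive is understandable. Adjustment for T does not recover the latent effect, however: the adjusted values there are −0.075 to −0.233.

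**Objectives seldom list covariates.** True, and adjusting for factors fixed before randomisation would raise no such objection. This covariate differs because treatment can change it.

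**Conclusion.** The concern holds. As written, section 11.3 produces for current pain a coefficient conditional on morphine timing, whereas section 1.2 and the summary state a comparison of randomised groups. This follows from the text and the algebra alone, given only that gabapentin changes morphine timing, as the trial's hypothesis implies, and that timing is associated with the score.

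The size and direction of the discrepancy cannot be determined from the documents. On assumed inputs it runs from negligible to substantial in either direction. It is a change in what is estimated when there is an effect; no false effect was seen when gabapentin affects neither pain nor morphine use. One secondary score is affected. The change should be made, but the primary morphine analysis does not depend on it.

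**What to change.** In section 11.3, replace the sentence on morphine timing with:

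> The main comparison of pain score right now will not include time since last morphine use; covariates, where needed, will be limited to factors fixed before randomisation, preferably the stratification factors (age category and baseline pain score).

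If the adjusted analysis is still wanted, add:

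> A model that also includes time since last morphine use will be reported only as a labelled sensitivity analysis, with a no-prior-dose indicator so that scores before any morphine are kept.

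The cost is one or two sentences, with no new data for the main analysis. The sensitivity model needs the time of the last dose, which section 6.2 and Appendix II do not list explicitly, although it may be captured. The main estimate will include the effect of rescue morphine, which can shrink the contrast (settings 3 and 4), and should be described that way, beside the morphine result.

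Precision may fall slightly. Over 1,000 simulated 60-patient trials the SD of the linear estimate was 0.267 without the covariate and 0.260–0.268 with it in setting 1, and 0.197 against 0.177–0.198 in setting 2.

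As a separate detail, the summary could say which daily score its average uses, so that it lines up with 11.3.

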12.0 OBTAINING INFORMED CONSENT

Eligible patients will be approached by a member of the study team regarding the study purpose, methods and design details. Both verbal and written assent and consent procedures will be completed in a private room and follow our institutional guidelines. Verbal assent will be obtained from participants 7 to less than 14 years old and written assent from participants 14 to less than 18 years old.

The consent/assent process will be documented in the medical record per institutional guidelines. Research participants and parents may decline participation without repercussions. Refusals will be documented in the research records and examined for any possible patterns. All research participants who meet eligibility criteria regardless of gender or minority status are fully eligible to participate in this study. All data will be kept confidential and stored in a locked file inside locked offices.

12.1 Consent at Age of Majority

The age of majority in the state of Tennessee is 18 years old. The PI/designee will identify study participants requiring consent at age 18 years. Active research participants must be consented at the next clinic visit after their 18th birthday.

APPENDIX I
EXAMPLE OF A SCHEDULE OF EVALUATIONS:

Upon confirmation of eligibility (any time between days 1 and 7 after qualifying vincristine dose, see section 3.0):

- Informed consent discussion
- Enrollment data obtained by study team
- Baseline pain assessment by study team
- Participant receives prescription for morphine PRN (see section 4.2)
- Participant is randomized and begins study drug (see section 4.1)

Enrollment through Day 21

- Daily pain assessment by study team
- Daily AE assessment by study team
- Refill morphine if needed
- Patient/family education regarding study drug

Day 21

- Complete last dose of study drug
- Complete last daily pain assessment and AE assessment
- Refer persistent pain to pain team or primary clinic for treatment as clinically indicated

APPENDIX II
RESEARCH ACTIVITIES

Study day	Confirm enrollment criteria	Informed consent	Randomization	VCR dose (expected or actual)	Pain score right now	Average Pain for 24h	Pain location	Pain descriptor	Order Morphine PRN	Study drug TID	Assess opioid use	Assess study drug use	Assess AE	Off Study
pre-enrollment				actual										
Diagnosis of NP (any day between 1 and 7)	x	x	x		x	x	x	x	x	x	x	x	x	
					x	x	x	x	x	x	x	x	x	
					x	x	x	x	x	x	x	x	x	
					x	x	x	x	x	x	x	x	x	
					x	x	x	x	x	x	x	x	x	
7				expected	x	x	x	x	x	x	x	x	x	x
8					x	x	x	x	x	x	x	x	x	x
9					x	x	x	x	x	x	x	x	x	x
10					x	x	x	x	x	x	x	x	x	x
11					x	x	x	x	x	x	x	x	x	x
12					x	x	x	x	x	x	x	x	x	x
13					x	x	x	x	x	x	x	x	x	x
14				expected	x	x	x	x	x	x	x	x	x	x
15					x	x	x	x	x	x	x	x	x	x
16					x	x	x	x	x	x	x	x	x	x
17					x	x	x	x	x	x	x	x	x	x
18					x	x	x	x	x	x	x	x	x	x
19					x	x	x	x	x	x	x	x	x	x
20					x	x	x	x	x	x	x	x	x	x
21					x	x	x	x	x	x	x	x	x	x

APPENDIX III PAIN ASSESSMENT TOOLS

The pain assessment scoring tools for this study are currently used at St. Jude in standard care as directed by the hospital policy; they are included here for reference purposes.

[figure not shown]
Assessment

- Always assume child's pain report is valid
- Infants and toddlers (less than age 4 years) or other children who cannot self report, use the FLACC Scale
- Score each component as a subscore (face, legs, activity, cry, consolability)
- Total subscores to determine FLACC score

FLACC scale

Categories	Scoring		
	0	1	2
Face	No particular expression or smile	Occasional grimace or frown, withdrawn, disinterested	Frequent to constant quivering chin, clenched jaw
Legs	Normal position or relaxed	Uneasy, restless, tense	Kicking or legs drawn up
Activity	Lying quietly, normal position, moves easily	Squirming, shifting back and forth, tense	Arched, rigid or jerking
Cry	No cry (awake or asleep)	Moans or whimpers; occasional complaint	Crying steadily, screams or sobs, frequent complaints
Consolability	Content, relaxed	Reassured by occasional touching, hugging or being talked to distractible	Difficult to console or comfort
Each of the five categories (F)Face; (L)Legs; (A)Activity; (C)Cry; (C) Consolability is scored from 0-2, resulting in a total score range of 0 to 10.			

- Older children (ages 4 to 7 years) who can self-report, use the Faces Pain Scale-Revised (FPS-R)

Say to the child, "The first face (*point to face 0*), has no pain. The last face, (*point to face 10*), has the worst pain ever. Point to the face that shows how you are feeling."

- Ages >7 years, Self report using a numeric scale 0-10 without reference to Faces Pain Scale-Revised (FPS-R)
